8.5. Baseline Smoking and Nicotine Testing

The following baseline data related to smoking will be summarized by treatment arm for both the All Randomized Set and the Safety Set:

- Average number of cigarettes smoked per day over 7 consecutive days, as reported in the subject diary
- Expired CO (ppm) at SV1
- Expired CO (ppm) at Day 0
- Cotinine result (ng/mL) at SV1.

If nicotine metabolism ratio (NMR) testing is done at SV1 then NMR will be derived as the ratio of the results for 3-hydroxycotinine (3-OH cotinine) and cotinine (ie, 3-OH cotinine / cotinine) and summarized by treatment arm.

8.6. Baseline Questionnaires

Questionnaire scores will be derived as described in Section [6.4.2](#).

The following will be summarized at baseline by treatment arm for both the All Randomized Set and the Safety Set:

- FTND: total score
- HADS: total score, anxiety score, depression score
- SEQ-12: internal stimuli score, external stimuli score, and total score.
- QSU-Brief: total score
- MNWS: total score.

8.7. Other Baseline Characteristics

Vital signs (body temperature, heart rate, and systolic and diastolic blood pressure) will be assessed at two timepoints prior to randomization: SV1 and Day 0. Baseline vital signs will be summarized by treatment arm for both the All Randomized Set and the Safety Set.

Serum chemistry and hematology testing will be performed at SV1. Baseline laboratory test results will be summarized by treatment arm for both the All Randomized Set and the Safety Set. Separate summaries will be provided for hematology tests (hemoglobin, red blood cells, white blood cells, neutrophils, lymphocytes, monocytes, eosinophils, basophils and platelets), serum chemistry tests (total protein, albumin, total bilirubin, aspartate aminotransferase (AST), alanine aminotransferase (ALT), alkaline phosphatase, glucose, sodium, potassium, calcium, creatinine and urea) and creatinine-clearance.

Urine pregnancy testing will be performed for all female subjects at SV1 and Day 0. Test results will be summarized by treatment arm and visit for all females in both the All Randomized Set and the Safety Set.

A 12-lead ECG will be performed at SV1. Baseline ECG findings (normal, abnormal – not clinically significant, abnormal – clinically significant) will be summarized by treatment arm for both the All Randomized Set and the Safety Set.

9. EXPOSURE TO STUDY TREATMENT

Study treatment consists of administration of study drug in combination with behavioral support.

9.1. Duration of Study Drug Treatment

The time (days) from randomization to first dose of study drug will be derived and summarized by treatment arm for the Safety Set.

Duration of study drug treatment (days) will be calculated as date of last dose of study drug minus date of first dose of study drug +1. Duration of study drug treatment will be summarized by treatment arm for the Safety Set. The number (%) of subjects who had duration of 84 days will also be summarized by treatment arm.

9.2. Study Drug Compliance

All subjects are planned to receive 3 doses of study drug each day for 84 days, for a total of 252 prescribed doses. If there are subjects that inadvertently enter in their patient diary taking more than the 252 prescribed doses, for the analysis 252 doses will be used. Per protocol, on a case-by-case basis, the study treatment may be reduced to twice a day. These dose reductions will only be allowed for subjects who experience moderate or severe adverse events that might be attributed to study drug and who would otherwise discontinue study treatment due to the adverse event. For subjects with a dose reduction, # doses prescribed is based on the number of days with 3 doses prescribed as well as the number days with 2 doses prescribed.

Each dose contains study drug (3 mg cytisinicline or placebo) in a single tablet.

For each dosing day (Day 1 to Day 84) subjects will record a diary entry for each dose: whether the dose was taken by the subject or missed and, for doses taken, the date and time of each dose.

The following variables will be calculated for each subject from the diary data and summarized by treatment arm for the Safety Set:

- total number of doses taken by the subject,
- total number of doses that were not taken (ie, missed)
- percentage of doses missed: (#doses missed / # doses prescribed) \times 100
- study drug compliance: [(# doses taken) / # doses prescribed] \times 100
- total dose of cytisinicline, calculated as number of cytisinicline taken \times 3 mg per dose
- Number and percentage of subjects with a dose reduction

Compliance with study drug will be summarized both as a continuous variable and as a categorical variable (<80%, 80-<90%, 90-<100%, 100%).

In addition to summary tables, details of study drug compliance will be listed. The listing will include the total dose of study drug (mg), total number of doses taken by the subject, total number of doses missed, percentage of doses missed, and percentage of doses taken (ie, compliance with study drug).

9.3. Behavioral Support Compliance

Twelve (12) behavioral support sessions are planned during the treatment period, Week 1 to Week 12 visits. Additional behavioral support will be provided during the follow-up period based on issues/concerns/questions raised by the subject.

The total number of behavioral support sessions received during the treatment period will be calculated for each subject and summarized by treatment arm for the Safety Set. Summaries will also be provided for compliance with behavioral support, derived as:

- [(# behavioral support sessions received) / (12)] \times 100.

10. EFFICACY ANALYSIS

The efficacy analyses will be conducted using subjects in the All Randomized Set. Unless otherwise specified, all randomized subjects will be included in efficacy analyses. Subjects will be evaluated by their randomized treatment arm ('intent-to-treat' analysis).

For qualitative endpoints, summary tables will present the number and percentage of subjects for each class of the endpoint. Quantitative endpoints will be summarized by presenting the mean, SD, minimum, median and maximum values. All summary statistics will be presented by treatment arm.

10.1. Analyses of Primary and Secondary Efficacy Endpoints

10.1.1. General Considerations

In general, the implementation of familywise error protection for a family of comparisons is most logically implemented using one-sided hypothesis testing because the tests must be interchangeable with respect to the goal of the research. The P values reported by statistical programs, unless otherwise indicated, will always be two-sided. A two-sided P value associated with a one-sided hypothesis is converted to a one-sided P-value for that hypothesis as follows: Let P be the two-sided P value. If the estimate associated with the hypothesis is consistent with the one-sided alternative hypothesis the one-sided P value is $P/2$, otherwise the one-sided P value is $1 - P/2$. Unless otherwise stipulated, one-sided P values will be used only to execute the Hochberg procedures for passing statistical criterion.

The overall Type I error probability for the trial is specified to be one-sided 0.025 (overall one-sided alpha). The primary objective has two endpoints therefore the interpretation of these analyses must protect the overall one-sided alpha of 0.025. The primary objective analyses will provide two one-sided P values. Assessing whether the primary objective meets statistical criterion will be implemented using the Hochberg procedure as follows. If neither one-sided P values are ≤ 0.025 then the primary objective will have failed to meet statistical criterion, whereas if both one-sided P values are ≤ 0.025 then both null hypotheses can be rejected and the primary objective will have met statistical criterion. If one of the one-sided P values is >0.025 then in order for the primary objective to meet statistical criterion the other one-sided P value must be ≤ 0.0125 ($=0.025/2$).

Secondary objectives will be analyzed only if a statistical criterion for the primary objective is met. Specifically, the amount of alpha passed to the secondary objectives will depend on the one-sided P values associated with the primary analyses (See FDA Guidance: Multiple Endpoints in Clinical Trials). There are three possibilities: (1) If the primary objective statistical criterion is not met then no alpha is left for the secondary analysis and the associated analyses of those endpoints cannot be associated with specified significance testing. (2) If both one-sided P values are ≤ 0.025 the amount of alpha passed to the secondary analyses is 0.025. (3) If one of the one-sided P values is >0.025 and the other is ≤ 0.0125 then the amount of alpha is based on the Hochberg procedures having been truncated and the amount of alpha that can be passed to the secondary analyses is 0.0125. (Note on truncated Hochberg when there are two hypotheses, the alpha to be passed is invariant to the fraction specification to be used in the computing of the alpha passed per FDA Guidance).

If case (2) happens (both primary comparisons are successful) then the Hochberg procedure based on one-sided 0.025 as described above can be used for secondary endpoints 1 and 2. Secondary endpoint 3 can be analyzed with multiplicity protection only if both secondary endpoints 1 and 2 are successful, and can be analyzed using one-sided significance level 0.025.

If case (3) happens (only one of the primary comparisons is successful) then the corresponding secondary endpoint can be analyzed using significance level one-sided 0.0125, and secondary endpoint 3 cannot be analyzed with multiplicity protection.

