In addition, the study will compare the safety profiles of 3 mg TID dosing for 6 weeks (Arm B) and 12 weeks (Arm C), relative to placebo (Arm A).

Objectives:

Multiple Primary Efficacy Objectives:

The multiple primary objectives are based on two comparisons where study success can be based on success for either comparison:

1. Assess whether subjects randomized to Arm B (3 mg cytisinicline TID for 6 weeks followed by placebo TID for 6 weeks plus behavioral support) have a higher probability of abstinence from Week 3 to Week 6 post-randomization as compared to subjects randomized to Arm A (placebo TID plus behavioral support).
2. Assess whether subjects randomized to Arm C (3 mg cytisinicline TID for 12 weeks plus behavioral support) have a higher probability of abstinence from Week 9 to

Week 12 post-randomization as compared to subjects randomized to Arm A (placebo TID plus behavioral support).

Secondary Efficacy Objectives:

The analysis for secondary objectives 1 and 2 will be done only if the corresponding primary comparison passes statistical criterion.

1. Assess whether subjects randomized to Arm B (3 mg cytisinicline TID for 6 weeks followed by placebo TID for 6 weeks plus behavioral support) have a higher probability of continuous abstinence from Week 6 to Week 24 post-randomization as compared to subjects randomized to Arm A (placebo TID plus behavioral support).
2. Assess whether subjects randomized to Arm C (3 mg cytisinicline TID for 12 weeks plus behavioral support) have a higher probability of continuous abstinence from Week 12 to Week 24 post-randomization as compared to subjects randomized to Arm A (placebo TID plus behavioral support).

The analysis for secondary objective 3 will be conditional and performed only if both primary comparisons 1 and 2 pass statistical criterion.

3. Assess for a reduction in risk of relapse from Week 6 to Week 24 in subjects receiving 3 mg cytisinicline for 6 weeks and then either continue 3 mg cytisinicline from Week 6 to Week 12 (Arm C) or were switched to placebo from Week 6 to Week 12 (Arm B). Subjects not abstinent at Week 6 will be regarded as having relapsed.

Other Objectives:

1. To compare arms (Arm B vs Arm A; Arm C vs Arm A) on 7-day point prevalence abstinence weekly at Week 2 to Week 12, then for Weeks 16, 20, and 24.
2. To compare arms (Arm B vs Arm A; Arm C vs Arm A) on serum cotinine levels every other week at Week 2 to Week 12, then at Weeks 16, 20, and 24.

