The primary analysis will include all randomized subjects by randomized arm (intent-to-treat analysis). The multiple primary comparisons will be for 6 weeks cytisinicline (Arm B) vs placebo (Arm A) and for 12 weeks cytisinicline (Arm C) vs placebo (Arm A). If the primary efficacy comparison meets statistical criterion, then the corresponding secondary efficacy outcome analyses will have formal meaning. The primary comparisons will be comparing the arms based on the ratio of the odds of success in the experimental arm divided by the odds of success in the control arm (odds ratio) using exact computations for stratified 2x2 frequency tables. The estimated odds ratio and exact confidence interval for the marginal 2x2 table across sites (unadjusted odds ratio), and the estimated difference in proportions and the associated derived exact confidence interval using the exact confidence interval on the odds ratio will also be reported.

Trial Size

The target accrual for each arm is planned for 250 (Approximately 750 for the study). The significance level to be used for the multiple primary comparisons is adjusted from the overall type I error probability of one-sided 0.025 to one-sided 0.0125 using the Bonferroni method to control for multiplicity. The assumed control arm probability of success (Weeks 9-24 abstinence) is 0.07 (7%). The hypothesized experimental arm minus control arm probability difference is specified as 0.12 (12%), corresponding to a hypothesized odds ratio of 3.12 (7% for placebo vs 19% for cytisinicline treatment). The statistical operating characteristics for each comparison are illustrated using simulation with 10,000 replicates. These specifications are consistent with 95.7% power for each comparison with, conditional on 0.07 control arm probability outcome, an odds ratio critical region of ≥ 1.83 , corresponding to a critical difference of ≥ 0.051 (7% for placebo vs 12% for cytisinicline treatment).

Safety

The profiles of adverse events for the arms with regard to incidences of treatment emergent adverse events will be assessed. Treatment emergent adverse events are defined as those events that appear during treatment or are present before treatment and subsequently worsen. Laboratory, vital signs and ECG data will primarily be assessed for clinical safety. Data will be listed and summarized for each treatment according to measurement time.

TABLE OF CONTENTS

SYNOPSIS	2
LIST OF TABLES.....	15
LIST OF FIGURES	15

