16.1. Statistical Design

The overall study type I error probability will be one-sided 0.025 conditional on evidence of a favorable outcome for cytisinicline. Subjects will be randomized with equal probability to one of three arms (groups), one of two experimental arms or a control arm. The intended dosing regimens in these three arms are placebo for 12 weeks (Arm A), 3 mg cytisinicline for 6 of 12 weeks (Arm B) and 3 mg cytisinicline for 12 weeks (Arm C). The details of the interventions are specified in Section 7.1 and Section 7.2.

Two primary study objectives are specified in Section 6.1. These two primary objectives specify that the outcomes for each of the two experimental arms are to be compared to the control arm. The study size is based on a one-sided type I error probability of 0.0125 for each comparison of an experimental arm to the control (placebo) arm. Study success will be assessed using the Hochberg method for the two comparisons and the overall study type I error probability of one-sided 0.025; the outcomes are assumed to be positively correlated.

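### SAP 10.1.1 tests the larger primary p-value at the full one-sided 0.025 and still passes 0.0125 to a Week 24 secondary when only one primary succeeds, so the overall 0.025 is not guaranteed

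*SAP*

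**What the plan says.** SAP 10.1.1 sets the overall type I error for the trial at one-sided 0.025. For the two primary p-values it uses Hochberg: if neither is at or below 0.025 the objective fails, "whereas if both one-sided P values are ≤ 0.025 then both null hypotheses can be rejected", and if one exceeds 0.025 the other must be at or below 0.0125. Protocol 16.1 agrees: "Study success will be assessed using the Hochberg method for the two comparisons".

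The same SAP section then sets out what is passed on:

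- Case (2), both primaries succeed: "If both one-sided P values are ≤ 0.025 the amount of alpha passed to the secondary analyses is 0.025".
- Case (3), only one succeeds: "the amount of alpha is based on the Hochberg procedures having been truncated", and 0.0125 is passed. The closing paragraph repeats this: "then the corresponding secondary endpoint can be analyzed using significance level one-sided 0.0125".
- A parenthetical note, attributed to FDA guidance, supports case (3): with two hypotheses, "the alpha to be passed is invariant to the fraction specification to be used in the computing of the alpha passed".

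No truncation fraction is given. The Protocol Synopsis (Primary Analysis) says that if a primary comparison meets its criterion, "then the corresponding secondary efficacy outcome analyses will have formal meaning". Protocol 6.2 and SAP 3.2 gate each continuous-abstinence secondary on its own primary but give no level for it.

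**The concern.** The two halves of SAP 10.1.1 describe different procedures. Testing the larger primary p-value at the full 0.025 is untruncated Hochberg. If that test fails, all the alpha has been offered to the primary family and none is left to pass. The SAP passes 0.0125 all the same.

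Study success may rest on either primary comparison (Protocol 6.1), so a single success followed by a formal Week 24 claim is a foreseeable outcome. In that outcome the stated 0.025 would not follow from the testing rule. The inconsistency can be seen from two adjacent paragraphs, and a repair made after unblinding would carry little weight.

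**Working it through.** **Inputs.** Overall one-sided alpha 0.025, Hochberg thresholds 0.025 and 0.0125, and 0.0125 passed in case (3) (SAP 10.1.1). 250 per arm, placebo 7%, difference 12 points (SAP 2.2). Positive correlation between the primary outcomes is assumed without a value (Protocol 16.1), so 0 to 0.5 is shown. Placebo rates come from the 7% sizing assumption, EAGLES US 6.7% with CI 5.3-8.4% (Protocol 16.5), and 8% for Weeks 5-8 in ORCA-1 (Protocol 4.3).

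**1. The primary family alone.** Under the global null with independent p-values, the chance of any rejection is 2(0.0125) - 0.0125² + 0.0125² = 0.0250. With bivariate normal statistics it is 0.0248 at correlation 0.25 and 0.0240 at 0.5. The stated 0.025 holds for the primaries.

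**2. Truncated Hochberg with two hypotheses and fraction g.**

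- Smaller p-value: [g/2 + (1-g)/2] × 0.025 = 0.0125, whatever g is.
- Larger p-value: c = [g + (1-g)/2] × 0.025 = 0.025(1+g)/2.
- Alpha passed if only one is rejected: a = 0.025 - c = 0.025(1-g)/2.

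Only the smaller-p threshold is free of g; the alpha passed is not.

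**3. Where the error arises.** Suppose one primary is effective enough to be sure to pass, the other primary is null, and the effective arm's Week 24 secondary is null. If the null primary has p ≤ c, it is falsely rejected. If it does not, case (3) applies and the secondary is falsely rejected when its p ≤ a. The error is P(p ≤ c or p_S ≤ a), which is at most c + a under any dependence and equals c + a - ca under independence.

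| Rule | c | a | Bound c + a | Corr. 0 | 0.25 | 0.5 |
|---|---|---|---|---|---|---|
| g = 0 | 0.0125 | 0.0125 | 0.0250 | 0.0248 | 0.0244 | 0.0232 |
| g = 0.5 | 0.01875 | 0.00625 | 0.0250 | 0.0249 | 0.0245 | 0.0236 |
| g = 1 | 0.025 | 0 | 0.0250 | 0.0250 | 0.0250 | 0.0250 |
| SAP | 0.025 | 0.0125 | 0.0375 | 0.0372 | 0.0364 | 0.0347 |

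The SAP takes c from g = 1 and a from g = 0. For the independent case: 0.0375 - 0.025 × 0.0125 = 0.0372.

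**4. Attained error with the planned test.** Site-stratified exact test, 250 per arm over 16 sites (10 with 16 per arm, 6 with 15), 100,000 replicates, SE 0.0005. *Nested* means that every placebo Week 24 success is also a placebo success in the null primary's window; *independent* means that the two placebo outcomes are unrelated.

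| Placebo rate, null primary / null secondary | Nested | Independent |
|---|---|---|
| 7% / 5.3% | 0.0233 | 0.0239 |
| 7% / 7% | 0.0229 | 0.0239 |
| 8% / 5.3% | 0.0232 | 0.0243 |
| 8% / 7% | 0.0236 | 0.0249 |
| 8% / 8% | 0.0235 | 0.0254 |
| 10% / 7% (assumed) | 0.0248 | 0.0260 |
| 15% / 10% (assumed) | 0.0265 | 0.0269 |
| 25% / 20% (assumed) | 0.0270 | 0.0288 |

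If the effective primary has the design effect of 12 points rather than certain success, the first five rows are unchanged (nested) or 0.0237 to 0.0250 (independent).

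On the higher rates: 8% of ORCA-1's 51 placebo subjects is about 4/51, exact 95% CI 2.2% to 18.9%. A placebo rate above 10% in a primary window is therefore not excluded.

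**5. How often case (3) occurs.** With both primaries truly 7% vs 19%, in 3.3% of trials if each placebo subject has the same outcome in both primary windows, and 4.2% if the two outcomes are independent (60,000 replicates). With an assumed 7% vs 15%, 18.6% and 29.5%.

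**The case against.** The strongest reply is that the gap is mostly theoretical.

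- **No excess at supported rates.** Every nested figure at the documents' rates is below 0.025. The highest independent figure, 0.0254, is within one standard error of it. This stands.
- **Nesting is the better model in one direction.** If Arm B's primary works and Arm C's is null, the secondary at risk is Weeks 6-24. SAP 4.1.2.1 requires verified abstinence through Week 12 for it, so placebo successes are essentially nested in Weeks 9-12 successes. With a shared placebo arm, the two test statistics then correlate at about 0.43 to 0.5 for the 7%/5.3%, 8%/7% and 7%/7% pairs. The relevant nominal figure is about 0.035, not 0.0372. This also stands, but 0.035 is still above 0.025. In the reverse direction, Weeks 12-24 success is not nested in Weeks 3-6 success, so independence is the limiting case.
- **The configuration is unlikely.** Arms B and C take the same drug through Week 6 (Protocol 7.2), so it would have to work in one arm's window and do nothing in the other's. This is agreed.
- **The note cites guidance.** That source is not available here, and nothing is said about what it contains. The arithmetic is enough to show that the note is wrong.

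These points limit the weight of the problem. They do not make the rule coherent: at low rates the 0.025 is kept by the discreteness of the exact test, which the SAP does not invoke as a safeguard.

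**Conclusion.** The concern holds. SAP 10.1.1 combines an untruncated threshold with an alpha transfer that belongs to Bonferroni, and the invariance note is incorrect. Nominal error in the affected configuration is 0.0347 to 0.0372 for correlations of 0.5 to 0, with a bound of 0.0375, against the stated 0.025.

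This is a lost guarantee, not a demonstrated inflation at planning rates. Attained error is 0.0229 to 0.0254 there and exceeds 0.025 clearly only at higher, assumed placebo rates. The primary family, the global null and the case where both primaries are effective are unaffected. What is exposed is a formal Week 24 claim made after only one primary succeeds. The correlations, the higher placebo rates and the 16-site layout are assumptions. It should be fixed, and the fix is simple.

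**What to change.** Before unblinding, delete the invariance note and adopt one coherent rule.

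**(a) Keep Hochberg at 0.025 and pass nothing in case (3).** Remove the reference to truncation and the 0.0125 from case (3) and from the closing paragraph of SAP 10.1.1, and report that secondary descriptively. In the Protocol Synopsis (Primary Analysis), limit the formal status of the secondaries to the case where both primaries succeed. The gating sentence "The analysis for secondary objectives 1 and 2 will be done only if the corresponding primary comparison passes statistical criterion" (Protocol Synopsis and 6.2, SAP 3.2 and 10.1.3) is not contradicted, because it states no level. It would still help to add there that a single success permits only a descriptive secondary analysis.

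**(b) State g and use matching levels.** Replace the 0.025 cut-offs on the primary p-values by c = 0.025(1+g)/2 in the Hochberg rule and in cases (2) and (3). Otherwise case (2) would still pass 0.025 when a primary p-value lies between c and 0.025. Replace the 0.0125 passed by a = 0.025(1-g)/2, and amend Protocol 16.1. Write out the case (2) rule for secondaries 1 and 2 in full, since it now refers back to the primary rule. If g = 0, also drop the claim in SAP 2.2 that power is underestimated.

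After either change the simulated error is 0.015 to 0.020 at all the rate pairs examined.

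**Cost.** The edits are text only, but Protocol edits go through the amendment process in Protocol 17.1. If the chosen rule departs from the Protocol, SAP 13 should say so. Option (a) leaves the primaries untouched and gives up a formal secondary in the case (3) trials counted above. Option (b) lowers the chance that both primaries succeed (figures are for identical / independent placebo outcomes):

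| True rates | Now, and under (a) | (b) g = 0.5 | (b) g = 0 |
|---|---|---|---|
| 7% vs 19% | 95.9% / 95.7% | 94.6% / 94.3% | 92.4% / 91.7% |
| 7% vs 15% (assumed) | 66.8% / 62.0% | 61.9% / 56.5% | 55.1% / 48.7% |

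At 7% vs 19%, at least one primary succeeds in 99.1% to 99.8% of trials under every rule. Option (a) is the simpler choice.
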